## ABSTRACT

Systemic lupus erythematosus (SLE) is chronic multifactorial autoimmune disease that affects many organs in human body. SLE patients have three times increased risk of mortality based on international data. Ethnic variation is known feature of the disease with important impact on patients mortality and morbidities. Descriptive studies from Saudi Arabia showed variation in clinical features from one region to another. However reliable inference from these studies is limited by study methodology, study size and lack of prospective cohorts. In addition, translational studies using biological samples to understand clinical phenotypes of SLE and response to treatments are lacking in Saudi Arabia and perhaps in Arab region. This is a proposed longitudinal prospective cohort study of Saudi SLE using open cohort study design to examine clinical characteristics and molecular phenotypes of Saudi SLE patients in relation to local environmental factors and local practices. We also aim to use the cohort as a nest for pragmatic randomised trial comparing efficacy of current treatment regimen of SLE in

Saudi population in the near future.

## INTRODUCTION

Systemic lupus erythematosus (SLE) is a chronic multi-system disease in which an underlying aberrant immune system leads to inflammation in various organs, and possibly consequent damage(1). Incidence and prevalence of the disease vary significantly from 1 -7 per 10000-patients to 19- 159 per 10000patients respectively in the united states(2-4). The estimated incidence in the united Arab of emirates is around 3.5 per 100000- patients and the prevalence is 109 per 100000 patients, while in Saudi Arabia the prevalence is

around 19 per 100000 patient. (1, 2) Such variation is likely due to use of different definitions, studies' standardization of age and racial background(2). Ethnicity is an important variable in disease occurrence, severity, phenotypic presentation and prognosis(5). For example; patients with African, Hispanic and Native American tend to have more severe disease and consequently increased mortality(5-7).

Unfortunately, national Saudi studies in SLE are sporadic and limited in addressing our unique population in prospective standardized fashion. The majority of the studies use retrospective chart review based designs that are threatened by potential selection and information biases. They also lack molecular and genetic data of Saudi patient with SLE. As a result, our understanding of Saudi SLE patients is limited. The knowledge gap can be categorized in several categories including:

- Descriptive clinical and molecular phenotype along with associated genotype. □  
Drug response, side effects and associated signature profile (molecular and genotype) □  
Outcomes of disease and its associated complications.
- Patients related research including patient related outcomes and qualitative type of research in Saudi population.

The importance of a national prospective cohort study to address the above mentioned knowledge gap is high, especially in the context of drug development and related clinical trials in which we are underrepresented.

## OBJECTIVES

The objectives of this cohort is to study Saudi SLE patients for the following:

1. Understand the molecular and genetic profiles, epigenetic, immunological and microbiome alteration in relation to various SLE phenotypes in Saudi Population.
  - a. Conduct whole exome sequencing for SLE patients to identify mendilian phenotypes including novel ones by enriching sequenced patients with patients who have strong family history of the disease.
  - b. Develop a baseline Saudi polygenic risk score for our SLE patients and compare it with Caucasian risk score in order to identify novel variations among our population. In addition, trying to explore the relationship of polygenic risk score and important clinical outcomes (disease remission, disease activity, disease damage and mortality).

Identify genetic and molecular signatures. (baseline genetic, proteomic and microbiome that differentiate various SLE clinical phenotypes from one another. By doing so, we might be to better differentiate various phenotypes and understand pathological mechanism behind the difference in clinical phenotypes.

2. To assess effect of environmental, social, medication and comorbidities on SLE important disease related outcomes including disease activity and disease damage.
  - a. Examine the relationship of presence of comorbidity (in particular diabetes, HTN and dyslipidemia on disease activity, disease damage and mortality.
3. To assess molecular and genetic/epigenetic signatures of response in relation to various treatment regimens in SLE.
  - a. Identify genetic and molecular medications related signatures. (genetic, proteomic and epigenetic modifications and microbiome alteration associated with changes in disease activity states from active to remission). This will allow us to have a holistic approach to SLE pathogenesis and may take us step further toward much more personalized medicine.
4. To assess long-term important outcomes of Saudi SLE population including determinants of disease damage, recurrent hospitalization and mortality.
5. Utilize the cohort as platform for nested pragmatic clinical trials within the cohort using cohort multiple randomized controlled trial design in the near future.

The cohort will focus on addressing all these aims in context of molecular, genetic, epigenetic and mycobiome data that will be collected periodically.

## RATIONAL

SLE disease in Saudi Arabia is yet not well defined especially in a population with high consanguinity and high inbreeding coefficient(3). Up until now, there has been no prospective cohort study for SLE patients in Saudi Arabia. As a result, current published literature is focused on retrospective chart reviews which are subjected to many forms of bias(4-6). In addition, these type of studies are difficult to utilize for translational research where clinical data are complemented by biological data collected at the same time. Studying disease characteristics in Saudi will provide better understanding of disease presentation, course

and outcomes especially if complemented by detailed immunological, molecular, genetic and microbiome data.

## METHODOLOGY

This proposed prospective registry that will follow open cohort study design. The following section details the inclusion and exclusion criteria, variables to be collected, biobanking and data management.

### PATIENTS RECRUITMENT AND ENROLLMENT:

Patients will be recruited from KSU-SLE specialized clinic. The clinic receive general referral from general rheumatology clinics in KSU and general referral from other clinics inside or outside KSU.

Inclusion criteria is the following:

- 1- Adult patients defined as > 18 years old.
- 2- Patients should fulfill one of the following classification criteria for SLE (ACR, SLICC or ACR/EULAR criteria).
- 3- No restriction on time of diagnosis.

Exclusion criteria:

- 1- Patients who don't fulfill classification criteria mentioned above.

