### COLLECTED VARIABLES:

#### Demographics

- Patient's ID (national, research, date, visit) sex, relationship status, educational level, work, gross monthly income, House (apartment, House) and house labor.

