#### GLOSSARY DEFINITIONS:

Please see the attached appendix for definition of variables in data collection form.

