## BUDGET AND SUPPORTING SERVICES

Estimated cohort enrollment is 40-50 new patient/year. Each patient will have two biological data collection for biobanking and four clinical data collection/year. The budget of this prospective cohort will be divided into:

- Research coordinator. (fulltime annual salary: 72,000)
- Data management and storage program. (in collaboration with Deanship of electronic communication, KSU innovation hub and CASIS, estimated cost is 10,000)
- Biobanking (Freezer, cost of blood withdraw, tubes, serum and cells separation, cells sorting, samples storage and microbiome collection and storage. (estimated cost is 70,000/freezer, 5000/year for samples biobanking).

Upfront cost for the first year is estimated to be 150,000 Saudi riyals. Estimated annual cost is around 80,000 Saudi riyals. Multiple grant approach will be used to maintain the fund until more secure mean of fund is allocated (such as a research chair).

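### Does a registry open at any disease duration lose age and disease duration because its printed variable list names neither?

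*Protocol*

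**What the plan says.** The Methodology section describes an open prospective cohort ("This proposed prospective registry that will follow open cohort study design") and introduces what comes next with the sentence "The following section details the inclusion and exclusion criteria, variables to be collected, biobanking and data management". Under Patients Recruitment and Enrollment, the third inclusion criterion is "No restriction on time of diagnosis", and the first requires an age above 18.

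Under Collected Variables, the Demographics entry gives identifiers followed by "sex, relationship status, educational level, work, gross monthly income, House (apartment, House) and house labor". The only date there stands in the bracket with the identifiers and the visit. The lists of exposures, examination findings, disease outcomes and patient-reported outcomes add no age, date of birth, date of diagnosis or onset, or disease duration.

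The Objectives need such variables. Objective 2a is "Examine the relationship of presence of comorbidity (in particular diabetes, HTN and dyslipidemia on disease activity, disease damage and mortality". Objective 4 covers long-term outcomes, "including determinants of disease damage, recurrent hospitalization and mortality". Objective 1b relates a polygenic risk score to outcomes that include damage and mortality.

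The list does not stand alone. Disease Outcomes sends the reader to a standardized data collection form for disease activity, and Glossary Definitions says "Please see the attached appendix for definition of variables in data collection form". Neither the form nor the appendix is in the text at hand.

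**The concern.** Patients who enter long after diagnosis have survived to that point and already carry damage. Age is an obvious confounder of any link between diabetes, hypertension or dyslipidemia and death, and disease duration is an obvious confounder of accrued damage. A diagnosis date is also needed to express survival from diagnosis with delayed entry, and to tell new cases from long-standing ones.

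The Methodology section presents the list as the detail of what is collected, and the list goes as far as house type and household help. Read literally, it suggests that two basic covariates were overlooked. That would be a data-collection gap, which no analysis plan could repair if the values did not exist. At stake would be a spurious comorbidity effect under objective 2a, and mortality figures misread as prognosis from diagnosis.

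**Working it through.** The Protocol gives no hazards, entry delays, event counts or sample-size calculation on this point, so there is no figure of its own to reproduce. Every rate below is assumed.

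**1. Is the omission real?** Yes. No list under Collected Variables names age, birth date, diagnosis date, onset or duration. Elsewhere age appears only as the eligibility threshold and in a background remark on standardization in the Introduction.

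**2. Is the list closed?** Set beside the rest of the Protocol, it is not:

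| Needed by the Protocol | In the printed list? |
|---|---|
| Diabetes, hypertension, dyslipidemia (objective 2a) | Not as diagnoses; only drugs taken for comorbidities |
| Hospitalization (objective 4) | No; admissions appear only among reasons for missed follow-up |
| Laboratory results (used for checking under Data Quality and Data Validation) | No |
| Item-level disease activity | Deferred to the data form |
| Age, diagnosis date | No |

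A list that omits the exposure of objective 2a and an outcome of objective 4 is a summary. Silence on age carries no more weight than silence on diabetes.

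**3. What if age really were absent?** Assume two age strata with 30% of patients older, comorbidity in 10% of the younger and a share p of the older, a death rate r times higher in the older, and no true comorbidity effect.

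- Older share among exposed: f1 = 0.3p / (0.3p + 0.7 × 0.1)
- Older share among unexposed: f0 = 0.3(1 − p) / (0.3(1 − p) + 0.7 × 0.9)
- Crude rate ratio = [1 + f1(r − 1)] / [1 + f0(r − 1)]

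With p = 0.3 and r = 2: f1 = 0.09/0.16 = 0.5625, f0 = 0.21/0.84 = 0.25, ratio 1.5625/1.25 = 1.25. With p = 0.5 and r = 4: f1 = 0.15/0.22 = 0.682, f0 = 0.15/0.78 = 0.192, ratio 3.045/1.577 = 1.93. The ratio is 1.00 if comorbidity or death does not vary with age. This calculation takes the comorbidity as recorded although it is unlisted, and age as unrecorded because it is unlisted. The two assumptions do not sit well together.

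**4. What of late entry?** Let S be survival from diagnosis (piecewise exponential) and let entry delay be uniform over 0 to W years. The 5-year risk from enrolment is ∫[S(u) − S(u+5)]du / ∫S(u)du, both over 0 to W. The risk from diagnosis is 1 − S(5).

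| Assumed hazard per year | From diagnosis | From enrolment, W = 5 / 10 / 15 |
|---|---|---|
| 3% throughout | 13.9% | 13.9 / 13.9 / 13.9% |
| 3% for 2 years, then 1.5% | 10.0% | 7.8 / 7.5 / 7.4% |
| 5% for 2 years, then 1.5% | 13.5% | 8.6 / 7.9 / 7.7% |
| 1% for 5 years, then 2% | 4.9% | 7.2 / 8.3 / 8.7% |

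The gap runs from 13.5 − 7.7 = 5.8 points low, through zero, to 8.7 − 4.9 = 3.8 points high. For determinants (baseline 3% then 1.5%), a factor tripling the hazard in the first 2 years only has a 5-year risk ratio of 2.02 from diagnosis, but 1.30 / 1.16 / 1.12 from enrolment. A constant hazard ratio of 3 is not attenuated: 2.71 against 2.79 to 2.80.

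These figures price the reading of one time origin as another. They do not measure a missing variable. The Protocol states no time origin and promises no estimate from diagnosis, and survival from enrolment is valid for the patients enrolled.

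**5. Would a diagnosis date rescue early disease?** Budget and Supporting Services says "Estimated cohort enrollment is 40-50 new patient/year", so five years bring 200 to 250 patients. With entry delay uniform over 0 to 10 years, about 0.20 to 0.22 of them enter within 2 years of diagnosis and contribute about 0.87 years each before year 2, which is roughly 35 to 45 person-years. At 3% a year that is 35 × 0.03 = 1.1 to 45 × 0.03 = 1.4 deaths; at 5%, 1.8 to 2.3. The early hazard would be almost inestimable even with perfect dates.

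**The case for a change.** The strongest case for a change is that the omission is certain on the text and that collection is a protocol matter. The Introduction itself partly attributes variation in published incidence and prevalence to standardization of age, and it faults earlier national studies for bias, so its own list might be expected to name age. Data Quality and Data Validation uses chart review to check variables, not to add them. For patients referred from outside the university, the chart may not hold a clear diagnosis date, so asking at enrolment is safer. The cost is trivial: two fields for 40 to 50 patients is 80 to 100 values a year.

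Part of this stands. The list would read better with both fields named, and a diagnosis date for outside referrals is the less secure of the two. It does not show that the data will be absent. Age must be checked for eligibility, the national identifier is held, and neither date changes with time, so both can be abstracted later if need be. This differs from an unmeasured time-varying exposure, which is lost once the visit has passed.

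**Conclusion.** No change to the plan is needed. The printed list does omit age and diagnosis date, but it is visibly a summary that defers to a form and glossary not at hand. It is equally silent on items the objectives cannot do without. Age is ascertained at entry in any case, and both dates are fixed facts that a registry team would record or retrieve as a matter of course.

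The possible distortion is not small if the fields were truly never held: a crude ratio of 1.25 to 1.93 for objective 2a under the assumed strata. That condition is not established. The late-entry figures rest wholly on assumed hazards, change sign with them, and concern a choice of time origin that the Protocol does not make. Delayed entry, damage counted as accrual after enrolment, and the labelling of survival estimates are commonly left to a statistical analysis plan.

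This conclusion assumes that the data form, or failing that the chart, supplies birth and diagnosis dates. Naming them in the Demographics list would be a courtesy to the reader; the design and the validity of its results do not depend on it.

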### COLLECTED VARIABLES:

#### Demographics

- Patient's ID (national, research, date, visit) sex, relationship status, educational level, work, gross monthly income, House (apartment, House) and house labor.

#### Exposures

- Family history (of SLE, other seropositive diseases or autoimmunity)
- Environmental (smoke inhalation, smoking, sun exposure, fasting, level of activity).
- infections (Bacterial (T.B, PJP, C.diff, altered gut microbiome, H-pylori), Viral (hepatitis B, C, HIV, CMV, EBV, HSV, VZV) fungal (candida), protozoal)

- medications/supplements (conventional DMARDs, Biological DMARDs, Synthetic DMARDs and other medications used for comorbidities)

#### Examination related variables

- The measurement of weight
- Height
- Blood pressure
- 66 Joint count (swollen, tender)  Back exam.
- Skin and mucosal exam
- CVS
- Respiratory
- Abdominal
- Neurological.

#### Disease outcomes

- Disease activity (system based from head to toe) (see standardized data collection form).
- Disease related damage.
- Cardiovascular disease (MACE), surrogate outcomes (carotid artery plaques using U.S), PAD.
- Osteoporosis (DEXA, fragility fracture (radiographic and symptomatic)).
- Malignancy.
- Renal failure requiring renal replacement therapy/renal transplant.
- Cognition (MME, MOCA)  Death/mortality.

#### Patient reported outcome

- PROMIS (version PROMIS-29 Profile v2.1) which include the following the assessment domains:
  - o Physical Function
  - o Anxiety
  - o Depression
  - o Fatigue
  - o Sleep Disturbance
  - o Ability to Participate in Social Roles
  - o Pain Interference
- LUPSQUAL

#### DATA COLLECTION PROCESS AND STORAGE:

Data will be collected using standardized data form (soft version is in the process of development). The form will be filled by trained individual (clinician or nurse joining the site) upon their joining of the clinical site. Training session will be conducted in standardized fashion using the glossary key for collected variables. Upon completion of data collection in each clinical visit, data will be transferred and stored in data storage program (Redcap, access or CAISIS). Data entry, cleaning, confirmation and retrieval will be handled by hired research coordinator.

Data will be collected regularly every 3 months (2-4 months). Research coordinator will ensure patients adherence to follow up protocol including attendance, data collection completion and rescheduling for missing visits.

Loss of follow up will be handled by direct communication with patients. Reasons of loss or missing follow up will be obtained using standardized data collection form through phone. Reasons include: death(reason of possible), being sick (type?), hospital admission(reason and where, records of admission should be retrieved), work, study, forgetfulness, travel, moving from city, loss of interest (due to symptoms remission, perception of poor management, follow up with another rheumatologist (why?), no specific reason).

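### Lost patients are traced only by phoning the patient, who cannot report their own death, so mortality is liable to be under-counted

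*Protocol*

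**What the plan says.** The protocol, under Data collection process and storage, sets clinical visits about every 3 months (2 to 4) and makes the research coordinator responsible for attendance and rescheduling. For patients who drop out it says: "Loss of follow up will be handled by direct communication with patients". It continues: "Reasons of loss or missing follow up will be obtained using standardized data collection form through phone". The list of reasons opens with death: "Reasons include: death(reason of possible), being sick (type". It goes on through hospital admission, work, travel, leaving the city and several forms of lost interest, among them a change of rheumatologist, and ends with "no specific reason".

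Mortality matters to the study's aims. Disease outcomes lists "Death/mortality". Objective 4 covers "determinants of disease damage, recurrent hospitalization and mortality", and objectives 1b and 2a also name mortality as an outcome.

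Two other places bear on the point. Demographics collects a national identifier ("Patient's ID (national, research, date, visit") but gives it no use for vital status. Data quality and data validation has each variable checked against charts, laboratory results and hospital reports at least every 3 months.

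**The concern.** The stated tracing method does not fit the first event it is meant to detect. A patient who has died cannot take the call. Unless someone else answers, the result is an unanswered phone, which looks the same as a living patient who has lost interest. The list has no entry for a patient who cannot be reached or whose vital status is unknown.

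At stake are the mortality count and everything built on it: the mortality part of objectives 1b and 2a and the determinants of mortality in objective 4. The gap is also hard to repair later, because a relative's contact details are easy to obtain at enrolment and difficult to obtain once the patient has been lost.

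**Working it through.** The protocol gives no sample size, death rate, loss rate or length of follow-up, so there is no figure of its own to reproduce. The main check is to look for any other route by which a death could become known.

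**Possible sources of vital status**

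- *Phone contact* (Data collection process and storage): the patient is the only informant named. No relative, proxy or number of call attempts is stated.
- *Outside admission records* (same section): these are retrieved, but they appear within the list of reasons learned by phone, so contact has to succeed first.
- *Data validation* (Data quality and data validation): this can reveal a death held in a chart or hospital report that the team can reach. It is described as checking variables, not as tracing lost patients.
- *National ID* (Demographics): collected, with no linkage to any death record stated.
- *Origin of patients* (Patients recruitment and enrollment): referrals come from inside and outside the institution. With moves and changes of rheumatologist foreseen as reasons for loss, death outside reachable records is a foreseeable event.

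No section shown closes the gap for deaths at home, elsewhere, or after transfer of care.

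**Effect on the number of deaths (illustration, assumed inputs)**

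Let f be the share of deaths outside reachable records and d the share of those learned of by phone, for example from a relative. Observed/true deaths = 1 − f × (1 − d).

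| f | d = 0 | d = 50% | d = 100% |
|---|---|---|---|
| 20% | 0.80 | 0.90 | 1.00 |
| 40% | 0.60 | 0.80 | 1.00 |
| 60% | 0.40 | 0.70 | 1.00 |

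The ratio never exceeds 1. The error in the count runs one way only, and is zero if every such death is reported by phone.

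**How many deaths there would be**

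Accrual of 40 to 50 patients a year comes from Budget and supporting services. With uniform entry over T years, person-years = accrual × T²/2. The annual death rate of 0.5–2% is an assumption.

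- T = 5: 40 × 25/2 = 500 to 50 × 25/2 = 625 person-years. Deaths: 500 × 0.005 = 2.5 to 625 × 0.02 = 12.5.
- T = 10: 40 × 100/2 = 2,000 to 50 × 100/2 = 2,500 person-years. Deaths: 2,000 × 0.005 = 10 to 2,500 × 0.02 = 50.

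**Effect on the rate**

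A rate also depends on person-time. If m is the share of deaths missed and p the share of person-time lost, observed/true rate = (1 − m)/(1 − p).

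- *Death causes the missed visit.* Person-time lost per death is at most about 4 months, the widest visit interval. Take 500 person-years and a 2% rate, so 10 deaths, with 2 missed: m = 0.20, p = (2 × 4/12)/500 = 0.0013, ratio = 0.80/0.9987 = 0.80. The rate falls by almost the full share missed.
- *Patient leaves first and dies later.* Person-time is lost too. With m = p = 20% the ratio is 0.80/0.80 = 1, so there is no bias. With m = 50% and p = 30% it is 0.50/0.70 = 0.71.
- If m is smaller than p, the ratio exceeds 1.

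**The case against.** The strongest reply is that the literal reading is strained. A phone form that asks about death, and its cause where possible, assumes that someone other than the patient may answer. This stands in part: it means deaths are liable to be missed, not that they will be. Relying on whoever picks up is still not a stated method.

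A second reply is that the data form, the glossary appendix and the consent form are referred to but not shown, and any of them could hold a next-of-kin field. That is possible. Even so, the protocol text states a different route and would need to be brought into line.

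A third is that validation against hospital reports is not limited to the recruiting hospital. This narrows the gap to deaths that no reachable record holds.

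A reader might go further and infer that the mortality rate will fall by 20–50%, so that the threefold excess mentioned in the Abstract ("SLE patients have three times increased risk of mortality based on international data") would show as 2.4 to 1.5. The documents do not support that. The shares are assumed, and the calculation keeps full person-time for patients after they are lost. At m = 50% and p = 30%, for example, 3 would become 3 × 0.71 = 2.1. The threefold figure is background, and no comparison with it is planned. Nor does it follow that any factor linked to leaving the clinic will look protective: remission, work and travel are also listed reasons for loss, and if low-risk patients leave and are censored at last contact, the rate can be biased upward. How to censor is a matter for an analysis plan and is not part of this point.

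**Conclusion.** The point holds in limited form. The protocol fixes one tracing route, and that route cannot by itself detect the first event on its own list, although mortality is a named outcome and objective. Deaths outside reachable records are liable to be missed, so the count of deaths is liable to be too low. The mortality rate is most exposed where the death itself causes the missed visit, because the event drops out and almost no person-time goes with it.

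The size cannot be derived from the protocol. The illustrations rest on assumed death rates, an assumed share of deaths outside reachable records and an assumed share learned of by phone. What they show is that deaths would be few, roughly 2.5 to 12.5 over five years on the assumed rates, so even a few missed deaths would be a material fraction. With so few events, determinants of mortality would be imprecise at five years even with complete tracing. This is a cheap improvement to data collection, not a defect that undermines the cohort.

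**What to change.** In Data collection process and storage, add a second source of vital status:

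1. Record one or two proxy contacts at enrolment.
2. When a patient cannot be reached, call the proxy and check vital status with the national ID already collected, against hospital records and, where access is granted, civil death records.
3. Record vital status, with unknown as its own category; the date of death or the date last known alive; and the source.

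The cost is a few fields on the data form, a line in the consent form covering proxy contact and record checks, an access request to the record holder, and some time from the full-time coordinator already in the budget, whose role already includes follow-up adherence. If access to civil records is refused, proxy contact still works.
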